**Appendix 1. Danish Society of Anesthesiology and Intensive Care Medicine (DASAIM)- score, modified.**

## Introduction

Post-surgery, patients are traditionally observed and treated in post-anesthesia care units (PACU) until they are discharged to the ward (or directly home) assessed by standardized international discharge criteria.

The research project "Why in PACU?" (Rigshospitalet, Denmark), has since the beginning of 2016 systematically collected and analyzed procedure-related complications in the recovery phase. The complications include pain, nausea/vomiting, circulatory and respiratory problems, orthostatic intolerance and cognitive disorders. Common to all the above-mentioned post-operative problems are the possible links to the inflammatory response caused by the surgical trauma.

Glucocorticoids can in this context be central for the reduction of acute postoperative organ dysfunctions, caused by the anti-inflammatory effect. In a number of different surgical procedures, single dose, pre-operative glucocorticoids have been shown to reduce post-operative nausea and vomiting (PONV), acute pain and need of opioids as well as accelerate the convalescence.

Meta-analyses also showed that single-dose administration of glucocorticoids (methylprednisolone and dexamethasone) for surgical patients is safe as opposed to long-term treatment.

Based on positive results in other procedure-specific studies, all mastectomy patients at Rigshospitalet, have received pre-operative high-dose steroids, in the form of 24 mg dexamethasone injection since mid-2015. This has resulted in a decrease in the proportion of patients who need observation in PACU from 30 % to 10 %. The reduction is primarily due to less pain, less sedation, and lower opioid administration.

Whether this is also partly due to a "systemic effect" (Hawthorn effect) as a result of increased focus on the area cannot be excluded.

Prior to creating clinical recommendations and standards, it is required that the results be tested in a randomized, controlled, clinical trial.

The study is not placebo-controlled since the positive effects of dexamethasone 8 mg on PONV have been shown in numerous trials and is already being administered to all patients at the clinic. It would therefore not be ethically correct to withdraw from this practice.

## **Aim**

The aim of this study is to investigate the effect of a single preoperative high-dose steroid injection on complications in the immediate postoperative phase after breast cancer surgery, with removal of the breast (mastectomy). Primary outcome is the proportion patients who require transfer to the post anesthesia care unit (PACU) and the proportion that can be transferred directly to the ward. Secondary outcomes are organ specific complications in the post anesthesia phase, pain and nausea the first 5 days, seroma and wound infection the first 14 days and readmissions the first 30 days after surgery.

The investigators hypothesize that the frequency of transfer to the PACU and organ specific complications will be lower among patients receiving high dose dexamethasone. The investigators hypothesize, that there will be no difference in wound infections, seroma or readmissions.

## **Outcomes**

### **Primary outcome**

The number of patients meeting criteria for postoperative transfer to the post-anesthesia care unit (PACU) according to the DASAIM-score (Appendix

### **Secondary outcomes**

- Discharge score in the operating room (according to discharge criteria, Appendix 1).
- Discharge score at arrival to the ward or PACU (according to discharge criteria, Appendix 1).
- Complications/adverse events in the ward the first 24 h or until discharge.
- Length of stay (PACU/Hospital)
- Pain, self-reported in patient questionnaire. Days 0-4.
- Nausea/vomiting, self-reported in patient questionnaire. Days 0-4.
- Analgetics and antiemetics, use of, self-reported in patient questionnaire. Days 0-4.
- Quality of sleep, self-reported in patient questionnaire. Days 0-4.
- Feelings of anxiety, restlessness, fatigue, self-reported in patient questionnaire. Days 0-4.
- Seroma, requiring drainage, the first 14 postoperative days

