## **Statistical Analysis Plan**

Categorical data are presented as numbers with percentages, and tests for significant differences between the groups are assessed with  $\chi^2$  test. Continuous data are presented as mean (95% CI) or as median with inter-quartile range or range and assessed for normal distribution with the Kolmogorov-Smirnov/Shapiro-Wilk test. Tests for significant differences between groups are performed with an independent-samples t-test or Mann-Whitney U test when appropriate. The primary outcome is evaluated using  $\chi^2$  test, and the different modalities in the discharge criterion system and length of stay (secondary outcome) are evaluated using the independent-samples Mann-Whitney U test. Need for seroma drainage, readmissions and wound infections are evaluated using  $\chi^2$  test.

All available data are used, missing data is not imputed. Data from the questionnaire on PONV and sleep is dichotomized into categories, PONV/no PONV and sleep problems/no sleep problems. A two-sided 5% significance level is chosen for the primary and secondary outcomes. To adjust for multiple comparisons in the tertiary outcome (questionnaire, 40 tests), we chose a Bonferroni corrected significance level of 0.125%.

Data analyses were conducted using SPSS for Windows, version 22 (IBM Corp., New York, USA).

Data processing is done by the investigator, who will continue to be blinded until all results are analyzed, and the abstract is written and accepted by co-authors.

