### **Clinical evaluations and outcome registration**

Pain (at rest) is evaluated on a numeric rating scale (NRS) by the patient, assigning pain a number between 0-10. Study personnel assign a score according to the criteria listed in appendix 1, where NRS 0 = 0 (no pain),  $0 < \text{NRS} \leq 3 = 1$  (light pain),  $3 < \text{NRS} < 7 = 2$  (moderate pain),  $\text{NRS} \geq 7 = 3$  (severe pain). If patients are not able to assign a number (e.g. due to sedation/doubt), it is accepted with a verbal rating scale (no/light/moderate/severe pain).

Nausea is evaluated by patients and assigned a score from 0 (no nausea) to 3 (severe nausea or vomiting).

Length of stay (hospital) is measured as time (hours and minutes) from start of the procedure until discharge from the ward.

Length of stay (PACU) is measured as time from arrival to PACU until the patient is deemed ready to transfer to the ward (as the actual transfer time depends on transport etc.).

The occurrence of seroma requiring drainage is recorded the first 14 postoperative days from patient records.

Readmissions for any reason, except planned procedures or oncological admissions, are collected from patient records for 30 days.

Side-effects and/or complications (any) are registered during hospital stay and up to 60 hours postoperatively. Adverse events/serious adverse events are defined according to ICH-GCP.

Patients receive a questionnaire to fill out on days 0-4. The elements of the questionnaire are:

- pain on average and at worst on the 11-point numeric rating scale (0 no pain, and 10 worst pain imaginable)
- nausea on average and at worst on the four-point numeric scale (0, none; 1, slight; 2, moderate; 3, severe) and vomiting (if any)

- use of analgesics
- feelings of sadness, restlessness or fatigue (yes/no)
- quality of sleep (good, difficulty falling asleep, frequent awakenings, no sleep)

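### The ward complications outcome has an observation window that depends on discharge and on location, both of which can differ by arm, although registration to 60 hours is already planned

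*Combined protocol and SAP*

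**What the plan says.** The Secondary outcomes section defines the item as "Complications/adverse events in the ward the first 24 h or until discharge". Under Clinical evaluations and outcome registration, the methods say: "Side-effects and/or complications (any) are registered during hospital stay and up to 60 hours postoperatively". Neither place says how the two periods relate, whether the word 'or' in the outcome means the earlier or the later time, when the 24 hours begin, or how events between discharge and 60 hours are found.

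Length of stay, in the PACU and in hospital, is another secondary outcome. The methods define the hospital part in fine units: "Length of stay (hospital) is measured as time (hours and minutes) from start of the procedure until discharge from the ward". The primary outcome is whether a patient meets the criteria for PACU transfer.

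The Statistical Analysis Plan names a test for three event outcomes ("Need for seroma drainage, readmissions and wound infections are evaluated using" chi-square) but does not name complications. Its general rule of chi-square for categorical data would presumably apply. It also states "A two-sided 5% significance level is chosen for the primary and secondary outcomes", and on incomplete data "All available data are used, missing data is not imputed". It makes no provision for unequal observation time.

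**The concern.** A comparison of event counts is fair when both arms are observed for the same time. Here observation ends at discharge, so a patient who leaves early has less time in which a complication can be counted. Time in the PACU is also outside the definition, so a patient sent there has a later start to ward observation. The trial expects the dose to change PACU transfer, and it measures stay as an outcome because the dose may change that too. Observation time is therefore a post-randomisation variable that may differ between the arms.

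At stake is the reading of one secondary outcome. The Aim section hypothesises that "organ specific complications will be lower among patients receiving high dose dexamethasone". A lower count in the 24 mg arm could be taken as support for this when it partly reflects shorter observation, or a real reduction could be hidden by the omission of PACU time.

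**Working it through.** **Plan's own figure.** The documents give no event rate, stay or power for this outcome. The only sample-size figure concerns PACU transfer. With unpooled variance it reproduces: (1.96 + 0.842)² × (0.3×0.7 + 0.1×0.9) / 0.2² = 58.9, so 59 per arm; 59 × 1.1 = 64.9, so 65 per arm and 130 in total. It serves below only as the group size.

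**The two texts side by side.**

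| | Secondary outcomes | Outcome registration |
|---|---|---|
| Location | Ward | Not restricted |
| End | 24 h or discharge | Hospital stay and up to 60 h |
| Events | Complications/adverse events | Any side-effect or complication |
| Collection after discharge | Not applicable to ward events | Not stated |

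If 'or' means the earlier time, observation is min(24 h, stay). If it means the later time, nothing after discharge can be a ward event, so observation is in effect the whole ward stay. Both depend on the stay.

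**Effect of discharge time with no true difference.** Assume the same hazard in both arms and 20% of patients affected by 60 h. Observed risk is 1 − exp(−H(t)), where H is the cumulative hazard.

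- Constant hazard: H(t) = λt, with λ = −ln(0.80)/60 = 0.00372 per hour.
- Hazard halving every 6 h: H(t) = A(1 − 2^(−t/6)), with A = 0.2231/(1 − 2^(−10)) = 0.2234.

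| Observation | Constant | Halving every 6 h |
|---|---|---|
| 24 h | 8.5% | 18.9% |
| 20 h | 7.2% | 18.2% |
| 8 h | 2.9% | 12.6% |
| Ratio, 20 h to 24 h | 0.84 | 0.96 |
| Ratio, 8 h to 24 h | 0.34 | 0.67 |
| Share of 60 h risk seen by 24 h | 43% | 94% |

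Changing the 60 h risk to 10% or 30% hardly moves the ratios: 0.84 and 0.34 to 0.35 with a constant hazard, 0.96 to 0.97 and 0.65 to 0.68 with halving. The shape of the hazard matters much more. For halving times of 4 to 12 h at 20% risk, the 20 h ratio runs from 0.99 to 0.92, the 8 h ratio from 0.78 to 0.51, and the share seen by 24 h from 99% to 79%.

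**Chance of a false significant result.** Assume instead a constant hazard with 20% risk over 24 h (λ = −ln(0.80)/24 = 0.00930) and 65 per arm. Power = Φ{(d√n − 1.96√(2p̄(1−p̄))) / √(p₁(1−p₁) + p₂(1−p₂))}, where d is the difference in risks and p̄ their mean.

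- 24 h against 20 h: 20.0% against 17.0%, about 6.5%.
- 24 h against 12 h: 20.0% against 10.6%, about 32%.
- Both arms at least 24 h, earlier-of reading: difference 0.

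These are chances of significance in favour of the shorter-stay arm, where the nominal value is 2.5% (half of the two-sided 5%).

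**Effect of leaving out PACU time.** At the planning rates of 30% and 10%, 0.30 × 65 = 19.5 control patients and 0.10 × 65 = 6.5 high-dose patients go to the PACU, about 13 more in the control arm. Their PACU hours are not ward time. If events cluster early, those hours carry a high hazard, and control events are undercounted. The documents give no PACU duration, so I put no figure on this.

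**Fixed window.** If H(t) is the same in both arms and t is the same for every patient, the expected difference is 0.

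**The case against.** The two periods need not conflict. Ward events in the first 24 h can be a subset of everything registered to 60 h, one serving as an outcome and the other as safety registration. That stands: a reader might infer a contradiction, or infer that events registered after the ward period are thrown away, and the documents say neither. But if the two are meant as subset and superset, the listed outcome still has the stay-dependent window.

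The size may also be small. The Aim section concerns the immediate postoperative phase, and events that cluster early make a few hours at the end of the window matter little, as the right-hand column of the table shows. A ratio of 0.34 needs a constant hazard, every patient in one arm leaving at 8 h, and every patient in the other observed for 24 h. Nothing in the documents suggests that pattern. The claim that a 24 h window misses more than half of the 60 h events likewise follows only from the constant hazard.

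The model also treats stay as independent of events. If a complication delays discharge, part of a shorter stay reflects fewer complications, and the difference is not wholly spurious. This stands too.

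Finally, other harm outcomes have fixed periods: 14 days for seroma and wound infection, 30 days for readmission. Safety does not rest on this one item.

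**Conclusion.** The point holds as a defect in the definition of one secondary outcome: its observation time depends on discharge and location, and either can differ by arm. A reader might go further and conclude that the plan biases a safety comparison towards 24 mg. The documents do not support that. They give no expected stay, the two mechanisms can pull in opposite directions, and discharge adds nothing under the earlier-of reading if all patients stay at least 24 h (the PACU omission would remain).

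For a 4 h difference in observation, the spurious ratio is about 0.84 to 0.96 under the two assumed hazard shapes. Larger differences in stay give more. These are illustrations rather than estimates, and they rest on equal hazards in both arms, one common stay within each arm, and stay unrelated to events. The change is worth making because it costs little and removes the dependence; confidence in any material bias is no more than moderate.

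**What to change.** Reconcile the two sections so that they state one window:

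- Define the outcome as at least one complication or adverse event from dosing to 60 hours postoperatively, for every patient, regardless of location or discharge.
- State that the 60-hour registration continues after discharge, and that events after discharge are collected by the same method and at the same times in both arms. Without this, a nominal 60-hour window could still change character at discharge.
- In the Statistical Analysis Plan, name the comparison: the proportion with at least one event, by chi-square.
- Keep ward events in the first 24 h as a description, stating when the 24 hours start and what 'or' means.

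The cost is slightly more follow-up work after discharge, so this is more than a change of wording. The outcome also becomes a different one, no longer specific to the ward, which is why the ward count is kept alongside it.

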## **Methods**

### **Study design**

Randomized, double-blind, controlled intervention study. Superiority design.

### **Randomization**

Computer generated, double-blind block randomization. Allocation ratio 1:1, block sizes (2,4,6,8) randomly vary and unknown to study personnel.

The allocation sequence with intervention details (24 mg or 8 mg dexamethasone) will be concealed in consecutively numbered (1-130), opaque envelopes by two other investigators not otherwise involved in the trial. Before sealing, 20 % of the envelopes are randomly controlled.

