### **Inclusion criteria**

- Planned unilateral mastectomy with or without axillary dessection
- Age 18 years or older
- Able to understand Danish or English and to provide informed oral and written consent.

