#### **Other collected data**

Demographical data (sex, age, height, weight, smoking status, use of alcohol, comorbidities), operative data (date and time of operation, diagnosis, duration of surgery, extent of axillary dissection, intraoperative bleeding). Type and dose of medication given by request.

All data are collected from patient record.

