#### **Sample size**

After modification of our ERAS protocol introducing high-dose glucocorticoids (125 mg methylprednisolone (equivalent to 24 mg dexamethasone) we observed a 30 % to 10 % decrease in PACU referral after mastectomy. To test the isolated effect of the increased glucocorticoid dosage in a well-implemented ERAS protocol, we chose to compare 24 vs 8 mg dexamethasone. Considering the observed 20 % absolute (66% relative) reduction in need for PACU transfer clinically relevant, a sample size of 130 patients (65 in each group) was calculated ([www.sealedenvelope.com](http://www.sealedenvelope.com)) with a two-sided 5 % significance level, a power of 80 % and an anticipated 10 % exclusion rate.

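### Axillary extent is recorded but left out of the PACU and seroma tests, which gives up some precision and protection against chance imbalance; it does not bias the comparison

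*Combined protocol and SAP*

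**What the plan says.** - **Inclusion criteria** pool two extents of surgery: "Planned unilateral mastectomy with or without axillary dessection".
- **Randomization**: "Computer generated, double-blind block randomization. Allocation ratio 1:1, block sizes (2,4,6,8) randomly vary and unknown to study personnel". No stratification factor is named, and the envelopes form one series numbered 1 to 130. The Procedures section assigns these numbers at enrolment.
- **Other collected data** lists "extent of axillary dissection" among the operative items.
- **Statistical Analysis Plan**: the primary outcome is compared by chi-square. For the wound and readmission outcomes, "Need for seroma drainage, readmissions and wound infections are evaluated using" the same test. No covariate, stratified test, subgroup or sensitivity analysis uses axillary extent. The general sentence on categorical data could cover a descriptive comparison of it, but that would not adjust either outcome.
- **Aim**: the hypothesis is fewer PACU transfers on the higher dose and no difference in seroma.

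**The concern.** Varying blocks keep the arm totals close. They do nothing for the mix of surgery within each arm. If axillary dissection affects PACU need or seroma drainage, a chance excess of dissections in one arm moves the observed difference, and the planned tests cannot take account of it. The trial is sized for about 80% power, so there is little to spare. If an imbalance appears and no adjustment was prespecified, any later choice to adjust will look data-driven. The trial already collects the variable needed to avoid this.

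**Working it through.** **Inputs from the documents.** Alpha: "A two-sided 5% significance level is chosen for the primary and secondary outcomes". Rates: "we observed a 30 % to 10 % decrease in PACU referral after mastectomy". Size: "a sample size of 130 patients (65 in each group) was calculated", "with a two-sided 5 % significance level, a power of 80 % and an anticipated 10 % exclusion rate".

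**Assumptions (the documents give no figures).** Share with dissection q = 20-50%; effect of dissection on PACU need g = 10, 20 or 30 points.

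**1. The plan's own figure.** With unpooled variance, n = (1.960 + 0.842)² × (0.3×0.7 + 0.1×0.9) / 0.20² = 58.9, so 59 per group. Then 59 × 1.1 = 64.9, or 65 per group and 130 in total. The stated size is reproduced. Power at 65 per group is 82.1% by formula and about 83% by simulation.

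**2. Chance imbalance at 65 per arm.** SD of the difference in share = √(2q(1−q)/65). The probabilities of 10 points or more are exact binomial; those of 15 or more are normal approximations.

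| q | SD (points) | 95% range (points) | P(≥10 points) | P(≥15 points) |
|---|---|---|---|---|
| 20% | 7.0 | ±14 | 15.3% | 3.3% |
| 30% | 8.0 | ±16 | 21.3% | 6.2% |
| 40% | 8.6 | ±17 | 24.4% | 8.1% |
| 50% | 8.8 | ±17 | 25.4% | 8.7% |

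**3. Shift in the risk difference.** If dissection has the same effect in both arms, shift = g × imbalance. At the 95% limits this is 1.4-1.7 points (g = 10), 2.8-3.4 (g = 20) and 4.1-5.2 (g = 30). The design difference is 20 points and its standard error is √((0.21 + 0.09)/65) = 6.8 points. At q = 40%, the SD of the shift is 0.1 × 8.6 = 0.86 points for g = 10 and 0.2 × 8.6 = 1.72 for g = 20. As shares of the variance these are 0.86²/6.8² = 1.6% and 1.72²/6.8² = 6.4%.

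**4. Validity of the unadjusted test.** Simulated trials with no treatment effect (30% in both arms, q = 30-50%) give overall type I error of 5.1-5.2%. Among trials with an imbalance of 15 points or more it is about 5.5-5.7% (g = 10), 7% (g = 20) and 9-10% (g = 30), while CMH stays near 5%.

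**5. Power at 30% vs 10%, q = 30-50%.**

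| g | Unadjusted, all trials | CMH, all trials | Unadjusted, imbalance ≥15 points against 24 mg |
|---|---|---|---|
| 0 | about 83% | about 0.1 point lower | not applicable |
| 10 | about 83% | 83-84% | about 78% |
| 20 | about 83% | 84-86% | 72-73% |
| 30 | about 83% | 86-88% | 66-67% |

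The lower end of each CMH range assumes a common odds ratio for treatment across strata, the upper end a common risk difference. With g = 30 the upper end needs 0.10 − 0.30q ≥ 0, so q of at most one third. In the trials of the last column (simulated with a common odds ratio), CMH keeps power at about 82-85%.

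**6. Seroma.** The shift formula is the same, but the documents give no seroma rate, so neither its standard error nor its power can be computed.

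**The case against.** The strongest reply is that nothing is invalid. Chance imbalance in a prognostic factor is part of the sampling error that the chi-square test already allows for, and step 4 confirms it. Blocked, unstratified randomisation with an unadjusted test is an acceptable design for a single-centre trial of 130. The average gain is small: for g = 10 it can be as little as 0.1 point of power. The poor conditional figures need a large effect and also an imbalance of 15 points or more against the 24 mg arm. That is roughly half of the 3-9% in step 2. All of this stands, and it makes this an inexpensive improvement rather than a defect.

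It also stands that no section says dissection raises PACU need or seroma. The size of the benefit is therefore conditional on g. The recommendation is less so, because CMH costs about 0.1 point if g is zero.

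A reader might infer three stronger things that the documents do not support:

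- **That the comparison is biased.** Randomisation protects it, and overall type I error holds.
- **That the envelopes should have been stratified.** This requires the axillary plan to be settled at enrolment. The inclusion criterion accepts both extents without saying so, and axillary extent is listed as operative data.
- **That imbalance would create or hide a seroma difference.** Without a seroma rate this cannot be shown.

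**Conclusion.** The point holds as one of precision and of protection against an unlucky allocation. A factor that splits the eligible population, and that the trial records, is unused in the two comparisons where it may matter. An imbalance of 10 points or more is quite likely (15-25%). Its usual consequence is modest against a 20-point design difference with a 6.8-point standard error. Stratified analysis raises power by somewhere between about 0.1 and 5 points, depending on the assumed effect of dissection and on how the treatment effect behaves across strata. These figures rest on 65 analysed per arm, 30% vs 10%, and the assumed q and g. For seroma the conclusion is qualitative only. The change is worth making, but the trial does not depend on it.

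**What to change.** Before unblinding, amend the SAP so that PACU transfer and seroma drainage are each tested with a Cochran-Mantel-Haenszel test stratified by axillary dissection (yes/no), in place of the plain chi-square, with the unadjusted test reported alongside. The amendment is best dated before the principal investigator receives the coded allocation list described under Blinding, because the arms can be compared from then on even with the doses hidden.

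State how the stratum is assigned: the planned procedure where the patient record shows it, otherwise the recorded extent. Note that the recorded extent is operative data obtained after randomisation, though under blinding. The planned procedure is not itself listed among the collected data, so this rule has to be written down.

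The cost is a short SAP addition and a check of the record for the planned procedure. About 0.1 point of power is lost if dissection turns out not to matter. Keep the randomisation, the envelopes and the sample size of 130 as they are.
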